3.2.2 Secondary Outcomes Measures

Outcome Measure	Measure Description	Time Frame
Modified Ashworth Scale (MAS)	The Modified Ashworth Scale assesses spasticity in patients with central nervous system lesions or neurological disorders. It provides a rapid and straightforward method for clinicians to evaluate spasticity while performing passive soft-tissue stretches.	Within the end of 4 weeks and 1-month follow-up of sham/real rTMS
Change on cortical excitability - motor evoked potentials (MEPs)	MEPs are electrical signals generated by stimulating the brain's motor cortex and recorded from muscles.	Within the end of 4 weeks and 1-month follow-up of sham/real rTMS
Mirror Movement Assessment Scale (MMAS)	This scale evaluates the presence and severity of involuntary mirror movements, where movement in one limb is mirrored by involuntary movement in the opposite limb. It provides a structured approach to quantify and monitor these movements, helping to gauge the impact of therapeutic interventions and track changes over time.	Within the end of 4 weeks and 1-month follow-up of sham/real rTMS
Adverse effects	Adverse effects of TMS-EEG can include temporary headaches, scalp discomfort, and mild skin irritation from EEG electrodes. Rarely, individuals might experience transient cognitive effects or muscle twitching. There is also a minimal risk of inducing seizures, particularly in those with a history of epilepsy.	Within the end of 4 weeks and 1-month follow-up of sham/real rTMS

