3.6.3 HD-EEG Recording

The HD-EEG setup involves placing electrodes across the scalp to monitor brain responses while applying rTMS. We will use a 64-channel system (eego mylab and Waveguard™ cap, ANT Neuro, Enschede, The Netherlands). This allows for precise mapping of the brain's electrical activity, enabling the investigation of changes in motor function and meta-plasticity induced by different rTMS frequencies in children with CP. See 5.1.2 for details of the HD-EEG.

3.6.4 rTMS

CP Participants in Experiment Group 1 will use rTMS using a figure-of-eight-shaped coil and rTMS stimulator (Nexstim, Finland) targeting the contralesional primary motor cortex. The intervention will consist of 10 sessions, each lasting 20 minutes, spread over four weeks. Each session will begin with priming: 10 minutes of 6-Hz rTMS at 90% of the resting motor threshold, delivered in two trains per minute (5 seconds per train with 25-second intervals between trains), totaling 600 priming pulses. This will be followed immediately by 10 minutes of 1-Hz rTMS at 90% of the resting motor threshold, delivered continuously without interruption, totaling 600 low-frequency pulses⁴⁷.

CP Participants in Experiment Group 2 will receive rTMS targeting the ipsilesional primary motor cortex. The intervention will consist of 10 sessions, each lasting 20 minutes, spread over four weeks. Each session will start with priming: 10 minutes of 6-Hz rTMS at 90% of the resting motor threshold, delivered in two trains per minute (5 seconds per train with 25-second intervals between trains), totaling 600 priming pulses⁴⁷. This will be followed immediately by 10 minutes of 10 Hz rTMS at 90% of the resting motor threshold, delivered continuously without interruption, totaling 2000 high-frequency pulses⁴⁸.

CP Participants in the Sham Group will receive rTMS by positioning the coil perpendicular to the scalp without delivering active stimulation, targeting both the contralesional and ipsilesional primary motor cortex. The intervention will consist of 10 sessions, each lasting 20 minutes, spread over four weeks. Each session will be divided into two parts:

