7. RESPONSE CRITERIA

7.1 Risks and Benefits

7.1.1 Risks

The participants in this study are not at all at risk. There are 3 types of possible dangers related to taking part in these studies: (i) discomfort from the MRI's magnetic field exposure, (ii) discomfort from the HD-EEG, and (iii) discomfort from rTMS.

Use of 3 Tesla (T) MRI: Every participant will use a Siemens Tim 3T Trio, an FDA-approved device. The 3T magnet has a bigger bore opening than the present system, which should lessen patient claustrophobia because gradient coil design has improved over the past few years. The FDA published guidelines on September 29, 1997, classifying these devices as "Non-significant risk devices." Since 1990, studies have safely used four Tesla (and higher field) scanners on human beings. While assessing the safety of an MR device, there are four main factors to consider. These include acoustic noise, dB/dt (time rate of change of magnetic fields), specific absorption rate (SAR) of radiofrequency (RF) energy, and static magnetic field strength. These are covered in more detail down below.

Static magnetic field strength: The strength of the static magnetic field distinguishes the three Tesla magnet systems. According to FDA rules, "significant risk devices" do not include field strengths up to 4 Tesla.

"The original MRDD Guidance stated a level of concern for static magnetic field strength of 2T. For the above 2T, a manufacturer was to provide evidence of safety. Clause 6.8.2 (jj) of the IEC 60601-2-33 states that examination of the whole body above 2T, or locally set limit, should be performed under an approved investigational human studies protocol, and vital body functions should be monitored. However, this requirement was published in July 1995. Since then, several research sites have been operating at field strengths up to 4T with no reported occurrence of adverse events. Consequently, operation up to 4T is not considered a significant risk."

Guidance for Submission of pre-market notifications for Magnetic Resonance Diagnostic Devices, Issued November 14, 1998
Food and Drug Administration

Center for Devices and Radiological Health

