Acoustic noise: The gradient field coils carry large, time-varying electrical currents during regular operation. The gradient coil in the static magnetic field is subject to force from these currents. The gradient coils produce an audible sound similar to a loudspeaker since they are not infinitely stiff and move slightly (about 100 microns) in response to these forces. This sound can be loud for some imaging sequences, such as echoplanar imaging, which this technique will use. The FDA has determined that a peak, unweighted sound pressure level of 140 dB represents a severe risk for acoustic noise in an MR system. This is not the sound level; the scan room is engineered to minimize acoustic reflections. For every MR scan, the MIC gives subjects headphones and earplugs, regardless of the system's sound intensity.

HD-EEG: HD-EEG has no known risks and is widely used in clinical and research settings. The non-invasive HD-EEG method is painless and uncomfortable. For all skin-contact physiological recordings, we shall use a hypoallergenic gel.

rTMS: Since TMS was first introduced in 1984, a number of side effects have been reported. The type of stimulation employed greatly impacts the likelihood of these side effects. To reduce the hazards as much as possible, the researchers will adhere scrupulously to all currently suggested safety precautions. When one pulse is administered at a time, as suggested in this study, there are no known negative effects or hazards associated with rTMS techniques. Hundreds of children have previously received a TMS or rTMS⁵⁸. Using this magnet can put a person in danger of having a seizure since it sends electromagnetic pulses through the brain. However, in the past, seizures have only happened in adult humans and animals when the magnet was employed for consecutive high-frequency impulses at a sustained level⁵⁹.

No children previously administered rTMS by the scientists experienced seizures or other notable neurologic problems. Numerous studies have shown that most children tolerate rTMS well⁶⁰⁻⁶². The various stimuli that can be used fall well within the boundaries of the most recent globally recognized safety standards. Risks, however, could include:

- a. **Headache and neck pain:** It is estimated that up to 20 out of every 100 TMS patients have Tightness in the neck muscles can cause headaches or neck pain. Acetaminophen (Tylenol®) quickly relieves discomfort in such situations.

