- b. Ringing in the ears:** When the stimulation coil's current is run through it, the TMS makes a loud clicking sound. This loud click may cause ear ringing and temporary hearing loss if no protection is used. Earplugs are used in the laboratory to prevent this possible negative effect. Research on humans and animals has shown that earplugs can significantly reduce the chance of experiencing hearing loss due to TMS.
- c. Seizure:** TMS can induce a seizure even in the absence of epilepsy, brain abnormalities, or other seizure risk factors. It is estimated that the total probability of this consequence is less than 1% for patients without any neurologic condition and between 1% and 2% for patients who have epilepsy. Nevertheless, the International Society for Transcranial Stimulation has identified this as a very worrisome consequence, and the professionals will make all necessary efforts to minimize the danger. It's crucial to remember that having a seizure brought on by rTMS has never increased the likelihood of epilepsy or caused seizures to follow. Seizures brought on by rTMS would happen either during or after the rTMS. It is not anticipated that seizures brought on by rTMS will happen hours or days later.
- d. Cognitive alteration:** Transient modifications in TMS may modify memory, attention, and other cognitive processes. This is a theoretical concern since no such adverse effects have been reported in any of the safety studies.
- e. Unexpected problems:** Although TMS has been utilized for more than 20 years in numerous laboratories worldwide, it is still an experimental therapy for the treatment of epilepsy, so unanticipated issues could arise.

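### The 10 Hz dose for experimental group 2 cannot be delivered as written (6,000 pulses by arithmetic, 2,000 stated), and two safety sentences in 7.1.1 need correcting

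*Protocol*

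**What the plan says.** **Dose (3.6.4).** Both active arms have 10 sessions of 20 minutes. Each session opens with the same priming block, "10 minutes of 6-Hz rTMS at 90% of the resting motor threshold, delivered in two trains per minute", with 5-second trains, 25-second gaps and a total of 600 pulses. Group 1 then receives 10 minutes of uninterrupted 1 Hz stimulation, totalled at 600 pulses. Group 2 receives 10 minutes of uninterrupted 10 Hz stimulation, totalled at 2,000. Sham Part 2 has 5 uninterrupted minutes at 10 Hz, totalled at 1,000, with the coil turned so that no active stimulation is delivered. Section 11.4 requires the study to be conducted exactly as the approved protocol describes, emergencies apart.

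**Risk text (7.1.1).** The section opens with "The participants in this study are not at all at risk". The next sentence introduces three types of possible danger: "i) discomfort from the MRI's magnetic field exposure, (ii) discomfort from the HD-EEG, and (iii) discomfort from rTMS". The rTMS paragraph says "When one pulse is administered at a time, as suggested in this study, there are no known negative effects or hazards". It then reports that past seizures occurred, in adults and animals, under sustained runs of consecutive high-frequency pulses. The itemised risks follow:
- Headache or neck pain: "It is estimated that up to 20 out of every 100 TMS patients have" this complaint, as the garbled sentence appears to mean.
- Hearing: "This loud click may cause ear ringing and temporary hearing loss if no protection is used".
- Seizure: "TMS can induce a seizure even in the absence of epilepsy".

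Section 3.2.2 adds, under adverse effects, "There is also a minimal risk of inducing seizures".

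**The concern.** The group 2 sentence fixes frequency, duration, continuity and pulse total, and the four do not agree. An operator cannot follow it exactly, and two operators could deliver doses that differ threefold while each believed they were compliant. This is the arm with the highest stimulation frequency in a paediatric trial. The mode it describes, sustained 10 Hz stimulation, is the kind that 7.1.1 itself associates with seizures. Whoever assesses the risk of this arm needs to know whether the 10 Hz block is a continuous run or a set of short trains.

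The 7.1.1 sentences are a smaller matter. The opening denies any risk, and the one-pulse sentence reassures about a mode that the active arms do not receive as treatment.

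**Working it through.** **1. Figures that reproduce.** Pulses = frequency × seconds of stimulation, with inputs from 3.6.4.
- Priming, active arms: 6 Hz × 5 s × 2 trains per minute × 10 minutes = 600. Stated: 600.
- Group 1 main block: 1 Hz × 600 s = 600. Stated: 600.
- Sham priming, each part: 6 Hz × 5 s × 2 × 5 minutes = 300. Stated: 300.
- Sham 1 Hz block: 1 Hz × 300 s = 300. Stated: 300.

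The same arithmetic therefore returns every total outside the 10 Hz sentences.

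**2. Figures that do not.**

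| Block | Frequency × time | Computed | Stated | Ratio |
|---|---|---|---|---|
| Group 2 | 10 Hz × 600 s | 6,000 | 2,000 | 3.0 |
| Sham Part 2 | 10 Hz × 300 s | 3,000 | 1,000 | 3.0 |

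**3. Whether any reading of the group 2 sentence fits.**
- Keep 10 minutes and no breaks: 6,000 pulses, so the total is wrong.
- Keep 2,000 pulses and no breaks: 2,000 / 10 Hz = 200 s. With 10 minutes of priming the session lasts 13 min 20 s, not 20 minutes.
- Keep 2,000 pulses and 10 minutes: the coil is active for 200 s of 600 s, one third of the time, so the block cannot be uninterrupted.

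No reading satisfies all the stated parameters. In sham Part 2, 1,000 pulses at 10 Hz last 100 s rather than 5 minutes.

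**4. Size.** 10 Hz pulses in group 2 over 10 sessions: 10 × 2,000 = 20,000, against 10 × 6,000 = 60,000. With priming, a session has 600 + 2,000 = 2,600 or 600 + 6,000 = 6,600 pulses.

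**5. The 7.1.1 sentences.** The no-risk sentence is contradicted by the sentence after it, by the itemised risks later in 7.1.1, and by 3.2.2. The one-pulse sentence is contradicted by 3.6.4. Single pulses are used for motor mapping (5.1.3) and for the TMS-EEG session that measures TEPs (3.6.4, including the TD children), but the intervention in the two active arms, 15 + 15 = 30 of 45 children with CP, is repetitive.

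At the protocol's upper rate of 20%, the expected number with headache or neck pain among those 30 is 0.20 × 30 = 6. This is an expected count at the highest quoted rate, not a cap: at that rate the binomial chance of more than 6 is 39%. It assumes that a figure for TMS patients in general applies to these children.

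**The case against.** The best defence concerns 7.1.1. The no-risk sentence is corrected at once, since the next sentence speaks of possible dangers and the section goes on to list headache, ear ringing, seizure, cognitive change and unexpected problems. The rTMS paragraph also says that side effects depend heavily on the type of stimulation, and it warns of seizure straight after the one-pulse sentence. The hearing risk is conditional on no protection, and earplugs and headphones are planned (5.1.3). Epilepsy is excluded (4.2.4), and 7.1.2 provides screening, monitoring and an emergency response. All of this stands, and it reduces the 7.1.1 part to a wording correction. It does not make the two sentences true.

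None of it answers the dose mismatch, which lies in another section and would remain if 7.1.1 were perfect.

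Three stronger readings are tempting, and the documents do not support them.
- A reader might infer that the protocol hides the risks. It does not: they are set out in the same section. Whether families see the faulty sentences is unknown, because the consent text is not available.
- A reader might infer that group 2 will receive 6,000 pulses per session, or that the dose breaches a safety limit. The text does not settle which parameter is wrong, and it gives no numerical limit to compare with.
- A reader might want an expected number of seizures. The protocol's rates are for patients without a neurologic condition (below 1%) and patients with epilepsy (1% to 2%). These children have CP and epilepsy is excluded, so neither rate describes them directly.

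**Conclusion.** The group 2 10 Hz block is wrong as written. Its stated duration and continuity imply 6,000 pulses per session against a stated 2,000, and no choice of parameter makes the sentence consistent with itself and with the 20-minute session. The conclusion rests only on multiplication of figures in 3.6.4. The affected exposure is that of the 15 children in group 2; sham Part 2 has the same threefold mismatch but no active stimulation. Because the dose of an active arm is left open in a mode that 7.1.1 links to seizures, it should be corrected.

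The two 7.1.1 sentences are also wrong as written, but of minor weight given the disclosure and mitigation elsewhere. Neither part affects the statistical analysis.

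**What to change.** **3.6.4.** The sponsor states the intended 10 Hz dose and makes pulse total, duration and train pattern agree in both 10 Hz sentences. There are three ways to do so:
- If 2,000 pulses in 10 minutes is meant, remove the statement that the block is uninterrupted and give train length and interval. For example, 20 trains of 10 s with 20 s gaps give 20 × 10 s × 10 Hz = 2,000 pulses in 20 × 30 s = 10 minutes. Ten such trains give 1,000 pulses in 5 minutes for sham Part 2. The example only shows that the numbers can agree; it does not recommend a dose.
- If 2,000 continuous pulses are meant, shorten the block to 200 s (100 s in sham Part 2) and correct the session length.
- If 10 continuous minutes are meant, correct the totals to 6,000 and 3,000, and review the risk text for group 2 against that dose.

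**7.1.1.** Delete the no-risk sentence. Limit the one-pulse sentence to motor mapping and the single-pulse TMS-EEG session. Naming headache or neck pain and seizure in the opening list would make it match the detail that follows. If the consent and assent forms repeat the text, correct them too.

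**Cost.** A wording amendment with IRB approval. If children in group 2 have already been treated, the dose they actually received should be documented. No change to arms, endpoints, sample size or analysis.

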7.1.2 Protection Against Risks

Several safety measures are included in the rTMS procedures to reduce danger for children. We will implement pre-session screening to assess the risk of adverse effects, including any history of seizures or neurological conditions that may contraindicate rTMS, and ensure continuous monitoring of the participant during the procedure, both in terms of physical well-being and the rTMS system's performance. Emergency first aid protocols are in place in the improbable event that a seizure happens, to stop it if needed. Moreover, in case of an emergency, the facility's medical alert protocol will be activated. A seizure brought on by an experimental method does not imply epilepsy in the person being studied. To accomplish this, a letter certifying that the seizure was caused experimentally would be supplied for any reason relevant to driving, insurance, or employment. Since surface electrodes will be placed over the muscle to capture the EMG, there won't be any problems with pain, infection, or bleeding. For TD participants, all

procedures follow the same safety protocols as for CP children including pre-screening for TMS contraindications and real-time monitoring for discomfort.

7.1.3 Benefits

The study offers several potential benefits for the subjects involved:

- **Improvement in Motor Function:** This study's primary aim is likely to explore the efficacy of different rTMS protocols on motor function. Participants may experience improvements in motor control, coordination, and overall physical abilities, which could enhance their daily activities and quality of life.
- **Meta-Plasticity Enhancements:** The study may induce beneficial changes in the brain's ability to reorganize and adapt, potentially leading to long-term improvements in neural connectivity and motor function. These changes can be significant for children with CP, who often face challenges related to motor function.
- **Access to Cutting-Edge Therapies:** Participants in the study may receive access to innovative and advanced therapeutic interventions that are not yet widely available. This could provide them with unique treatment options that positively impact their condition.
- **Contribution to Scientific Knowledge:** By participating in this study, subjects and their families contribute to research that could benefit future children with CP. The findings from this study may help develop more effective treatments and interventions for others with similar conditions.
- **Monitoring and Support:** Medical professionals often closely monitor participants throughout the study, which can lead to early detection of any issues and provide additional support to the child and their family.

While these benefits are potential outcomes, it's important to note that they may vary depending on the individual response to the intervention.

8. ADVERSE EVENTS AND SERIOUS ADVERSE EVENTS

8.1 Adverse Event Monitoring

Adverse event data collection and reporting, which are required as part of every clinical trial, are done to ensure the safety of subjects enrolled in the studies as well as those who will enroll in future studies using similar agents. Adverse events are reported in a routine manner at scheduled times during a trial. Additionally, certain adverse events must be reported in an expedited manner to allow for optimal monitoring of patient

safety and care. Adverse events will be coded and reported using the MedDRA dictionary.

All patients experiencing an adverse event, regardless of its relationship to study drug/device, will be monitored until:

- the adverse event resolves or the symptoms or signs that constitute the adverse event return to baseline;
- any abnormal laboratory values have returned to baseline;
- there is a satisfactory explanation other than the study drug for the changes observed; or
- death.

8.2 Definitions

8.2.1 Definition of Adverse Event

An adverse event (AE) is generally defined as any unfavorable and unintended diagnosis, symptom, sign (including an abnormal laboratory finding), syndrome or disease which either occurs during the study, having been absent at baseline, or if present at baseline, appears to worsen. Adverse events are to be recording regardless of their relationship to the study intervention.

8.2.2 Severity of Adverse Events

The severity of an AE is graded as follows:

Mild (grade 1): the event causes discomfort without disruption of normal daily activities.

Moderate (grade 2): the event causes discomfort that affects normal daily activities.

Severe (grade 3): the event makes the patient unable to perform normal daily activities or significantly affects his/her clinical status.

Life-threatening (grade 4): the patient was at risk of death at the time of the event.

Fatal (grade 5): the event caused death.

8.2.3 Serious Adverse Events (SAE)

A “serious” adverse event is defined in regulatory terminology as any untoward medical occurrence that:

- Results in death.

If death results from (progression of) the disease, the disease should be reported as event (SAE) itself.

- Is life-threatening.
(The patient was at risk of death at the time of the event; it does not refer to an event that hypothetically might have caused death if it were more severe).
- Requires in-patient hospitalization or prolongation of existing hospitalization for ≥ 24 hours.
- Results in persistent or significant disability or incapacity.
- Is a congenital anomaly/birth defect
- Is an important medical event

Any event that does not meet the above criteria, but that in the judgment of the investigator jeopardizes the patient, may be considered for reporting as a serious adverse event. The event may require medical or surgical intervention to prevent one of the outcomes listed in the definition of “Serious Adverse Event”.

For example: allergic bronchospasm requiring intensive treatment in an emergency room or at home; convulsions that may not result in hospitalization; development of drug abuse or drug dependency.

